3. STUDY DESIGN

Design

The Girls United cRCT aims to evaluate the effectiveness of the Girls United program, a school-based intervention blending targeted mindfulness and psychoeducation. Delivered by trained and experienced mindfulness health professionals, the program is compared to a teaching-and-care-as-usual (TAU) approach. The study includes two groups: (1) an intervention group where girls' friendship dyads participate in the Girls United program, and (2) a control group where girls' friendship dyads receive TAU.

Duration

The 14-week Girls United program will be delivered in two cohorts across two academic years: cohort 1 in 2025–2026 and cohort 2 in 2026–2027. The program will run in four phases from October 2025 to May 2026 for both cohorts. Baseline measurements (T0) will occur in September 2025 for cohort 1 and February 2026 for cohort 2. Subsequent measurements include T1 (November 2025 for cohort 1 and April 2026 for cohort 2), T2 (January 2026 for cohort 1 and June 2026 for cohort 2), T3 (March 2026 for cohort 1 and October 2026 for cohort 2), and T4 post-intervention measurements (May 2026 for cohort 1 and December 2026 for cohort 2). A long-term follow-up measurement (T5) will be conducted in May 2027 for cohort 1 and December 2027 for cohort 2 (see Figure 1).

Setting

The study will take place at mainstream primary schools of school partnerships such as RiBA, BLICK op onderwijs and Scholennetwerk BSI and schools that are involved via our social media channels and webinars. These schools will be broadly representative of Dutch mainstream primary schools with respect to the type of school (urban/rural, large/small) and high/middle/low Socio Economic Status (SES) of the school.

[figure not shown]

Figure 1. Flowchart of study assessment time points for cohort 1 and 2.

4. STUDY POPULATION

4.1 Population

The study population will consist of high-risk friendship dyads who are primarily characterized by high levels of co-rumination within their daily interaction patterns. “High risk” is defined on the dyadic level and implies that at least one of the two girls of one friendship dyad, or both girls, should have a score above the median co-rumination screening score of the cohort the dyad belongs. The study collaborates with school partnerships such as RiBA, BLICK op Onderwijs, and Scholen-netwerk BSI, with most friendship dyads expected to be drawn from the upper grades of mainstream primary schools within these networks.

4.2 Inclusion criteria

To be eligible for inclusion, a *participant/girl* must meet all of the following criteria:

- 1) Aged 10 to 12 years.
- 2) Visiting a primary school of RiBA, BLICK op Onderwijs, and Scholennetwerk BSI (i.e., collaborative school network).
- 3) Attending 5th or 6th grade of mainstream upper primary education in academic year 2025/2026 or 2026/2027.
- 4) Being a cisgender woman or being a transgender woman.
- 5) Having a good or best friend (being a cisgender woman or being a transgender woman) at the same school.

To be eligible for inclusion, a *dyad/girls* must meet the following inclusion criteria:

By lack of an official cut-off score for high co-rumination levels, we will base our inclusion on a distribution-based technique. That is, we will include friendship dyads of which at least one of the two girls, or both girls, have a score above the median co-rumination screening score of the cohort on the Co-rumination Questionnaire-Short (Hankin, Stone & Wright, 2010). This will result in a sample of the 50% highest scoring girls on co-rumination. Note that a distribution-based technique is a common-used technique to select a high-risk population of clinical significance in the absence of meaningful clinical cut-offs (Sloan, Symonds, Vargas-Chanes & Fridley, 2003).

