8.3 Study procedures

Measures

Questionnaires T0, T1, T2, T3, T4 and one-year follow-up T5

For the dyad girls, filling out the T0 questionnaires will take place via BigBlueButton, so that the girls the first time that they have to fill out the questionnaires will be able to ask questions about the items and the researchers will be able to assist. Both girls of a dyad will receive a link to the BigBlueButton environment via email. Via BigBlueButton it is possible to deliver the questionnaires via the chat-function. Both girls of a dyad will fill out their own questionnaires independently.

Girls, parents/main caretakers, and trainers will receive online questionnaires via email at the follow-up timepoints (T1, T2, T3, T4), and one-year follow-up (T5). A trained PhD student or senior research assistant will be responsible for distributing all questionnaires via Qualtrics. If participants do not respond within one week, a reminder email will be sent. Three days later, those who still have not completed the questionnaire will receive a follow-up phone call from the trained PhD student or senior research assistant. Teacher-mentors will assist by sending the reminder emails, while the trained staff will handle the phone calls. The estimated time burden for completing the questionnaires is detailed in Table 1 for girls, Table 2 for parents/main caretakers, and Table 3 for trainers.

Table 1. Specified duration: girls.

Questionnaire	Duration (min)
Screening	
Co-rumination Questionnaire – CRQ short	2
Total	2
T0 t/m T4 and follow-up primary outcome measures	
Co-rumination Questionnaire – CRQ short	2
Total	2
T0 t/m T4 secondary outcome measures	
RCADS (Subscale Generalized Anxiety Disorder)	2
CDI-2	10
PANAS-C	5
CoDEQ	5
NRI	10
CBSK	6

Total		38
T0 t/m T4 and follow-up: moderator		
Total		2
T0 t/m T4 and follow-up: mediators		
MAAS-A		5
CAMM		5
DERS		10
Total		20
T1 t/m T4 implementation variables* only for girls in the intervention condition		
Participant responsiveness		14
Practice outside of the training session		7
Total		21.5
Total Screening (min.)		2
Total T0 t/m T5 (min.)	60 x 6 =	360
Total implementation measures. only for girls in the intervention condition (min)		21.5

Table 2. Specified duration: parents/caretakers.

Questionnaires	Duration (min)
T0	
Descriptives (SES)	2
Total	2
T0 en T4	
Parental health care use of their child/family	3
Total	3
T0, T2 en T4 : Implementation variables	

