In this study, following psychotherapy literature, the potential for harm is defined as sustained deterioration in a girl's functioning that is *attributable to the prevention program* (Duggan et al., 2014). Evidence-based mindfulness programs are commonly described as educational or skills training programs, rather than forms of psychotherapy, but are often used to reduce psychological symptoms and stress in (sub)clinical populations. The literature on harmful effects of mindfulness programs is sparse. To be able to manage (potential) harm caused by the online training sessions skillfully and in a protocolled manner, we developed a risk management protocol to provide a consistent approach to the identification, reporting and follow-up of risks related to participation in the intervention condition. Before the first training session starts, the trainers explain that the girls are not allowed to talk about suicide, self-injury, sexual or physical abuse or eating disorders because of safety reasons. When girls talk about suicide, self-injury, sexual or physical abuse or eating disorders during the online training sessions, the trainer will stop the session. In these cases, the coordinating researcher will immediately (by no contact within 24 hours) contact the PI. The PI will contact the independent health care professional in case of severe problems. Depending on the situation, parents/main caretakers of both participants of the dyad or the school-mentor will be informed by the PI, depending on the specific topic. The PI will inform parents/main caretakers in situations of non-family related acute problems and will advise them to contact the family doctor or the independent health care professional. In case of severe family-related problems, the PI will call inform the school-mentor. We will inform the mentor in case of family-related acute problems, so that the school will be able to decide to use the Veilig Thuis Protocol. In severe cases the independent health care professional will also be consulted by the PI. In all situations, we protect the privacy of all participants. This implies that we only should inform parents/main caretakers or the mentor more in-depth when the participant initiated the conversation about suicide, self-injury, sexual or physical abuse, substance abuse or eating disorders. The training sessions will be continued after this procedure. All reported difficulties and support provided will be logged in the research team logbook. This part of the intervention protocol will be discussed and agreed with the headteachers/teacher-mentors of the participating dyads and will be explained in the participant information sheets for parents and girls. Moreover, following

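### Cohort 2's calendar contradicts itself, and on its stated wave dates girls in 6th grade at baseline leave primary school between T2 and T3, mid-programme, which the protocol does not address

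*Protocol*

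**What the plan says.** **Eligibility (protocol 4.2).** Criterion 2 requires "Visiting a primary school of RiBA, BLICK op Onderwijs, and Scholennetwerk BSI". Criterion 3 requires "Attending 5th or 6th grade of mainstream upper primary education in academic year 2025/2026 or 2026/2027". Criterion 5 requires "Having a good or best friend (being a cisgender woman or being a transgender woman) at the same school". None of these differs by cohort.

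**Calendar (protocol 3, Duration).** "Baseline measurements (T0) will occur in September 2025 for cohort 1 and February 2026 for cohort 2". The later waves include "T2 (January 2026 for cohort 1 and June 2026 for cohort 2") and "T3 (March 2026 for cohort 1 and October 2026 for cohort 2"). Cohort 2's T4 is December 2026 and its T5 December 2027. The same paragraph assigns cohort 2 to academic year 2026-2027 and has the programme running from October 2025 to May 2026 for both cohorts. Section 5.1, on training the trainers, also puts cohort 2's sessions in 2026/2027. The Summary places T1 to T3 during the programme or TAU, and T4 directly after it.

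**School-based contacts.** Section 8.3 states: "Teacher-mentors will assist by sending the reminder emails, while the trained staff will handle the phone calls". Section 9.2.2 lets trainers seek advice from teacher-mentors and states: "In case of severe family-related problems, the PI will call inform the school-mentor".

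**Randomisation and analysis.** Section 8.2 describes 1:1 block randomisation of dyads and names no stratification by grade or cohort. The growth models in sections 10.1 and 10.2 name intervention arm as the exogenous predictor.

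**The concern.** The programme is delivered to a pair of friends, and the primary outcome asks how that pair talks about problems when they meet. Section 1 justifies a school-based programme by the time the friends spend together at school. If two friends part after the summer, co-rumination and friendship quality at T3 and T4 can change for reasons unrelated to the programme. TAU is defined in section 5.1 as unchanged regular education, which a move to secondary school also alters.

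Losses also come in pairs: under section 8.4, once one girl withdraws, no more data are collected from her or her friend.

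On the stated wave dates this would affect only one of the four cohort-by-grade groups before T4. The protocol has no provision for it.

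**Working it through.** The protocol gives no figure on this point to reproduce, so the check sets the calendar against the grade criterion.

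**Inputs.** Wave dates are from section 3. Two assumptions are not stated in the protocol: a school year from August to July, and 6th grade as the last primary year. The second is implied by section 4.2 (upper primary education) and by section 11.2, which recruits from primary-school grades 7 and 8 in Dutch numbering.

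**Step 1: grade at each wave.** The grade rises by one at each new school year.

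| Wave | Cohort 1 date | Grade if 5 / 6 at T0 | Cohort 2 date | Grade if 5 / 6 at T0 |
|---|---|---|---|---|
| T0 | Sep 2025 | 5 / 6 | Feb 2026 | 5 / 6 |
| T1 | Nov 2025 | 5 / 6 | Apr 2026 | 5 / 6 |
| T2 | Jan 2026 | 5 / 6 | Jun 2026 | 5 / 6 |
| T3 | Mar 2026 | 5 / 6 | Oct 2026 | 6 / left |
| T4 | May 2026 | 5 / 6 | Dec 2026 | 6 / left |
| T5 | May 2027 | 6 / left | Dec 2027 | left / left |

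For cohort 2 girls in 6th grade at baseline, 2 of the 5 waves to T4 fall after primary school, including the post-intervention wave. In both cohorts the gap between successive waves up to T4 is 2 months, except cohort 2's T2 to T3, which is 4 months.

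**Step 2: conflict within the calendar.** Section 3 makes three statements about cohort 2 that cannot all hold: it belongs to 2026-2027; its programme ends in May 2026; its T0 to T4 run from February to December 2026. If the programme ended in May 2026, T2 (June) and T3 (October) could not fall during it, as the Summary says they do. If cohort 2 ran wholly inside 2026/2027, no girl would change school before T4.

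**Step 3: share of the sample.** Exposed dyads = 160 × (share in cohort 2) × (share of those in 6th grade).
- Equal cohorts and grades: 160 × 0.5 × 0.5 = 40 dyads, 25%.
- Both shares 0.4: 160 × 0.4 × 0.4 = 25.6, about 26 dyads, 16%.
- Both shares 0.6: 160 × 0.6 × 0.6 = 57.6, about 58 dyads, 36%.

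The allowance for loss to follow-up in section 4.4 is 160 − 122 = 38 dyads. The exposed group is of about that size in the equal case, though not all of it would be lost.

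**Step 4: balance between arms.** Take 80 cohort 2 dyads, 40 in 6th grade, 40 allocated to each arm without stratification. The number of 6th-grade dyads in one arm has mean 20 and SD = √(40 × 0.5 × 0.5 × 40/79) = 2.25. A split of 24 v 16 is 4/2.25 = 1.8 SD from even. Under this hypergeometric distribution a split that uneven or worse has probability 0.12, and 74% of allocations lie within 22 v 18. This is ordinary chance imbalance.

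**The case against.** **Eligibility.** A reader might infer that these girls cease to be eligible at T3 and T4. The protocol does not support that. Section 4.2 sets entry conditions, nothing requires them again at later waves, and attending 6th grade in 2025/2026 satisfies criterion 3 permanently.

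**Bias.** A reader might also infer that the move biases the comparison between arms. It does not do so systematically: dyads are randomised 1:1, so the move is balanced in expectation, and step 4 shows that large chance imbalance is uncommon. The fallback in section 8.2 to randomising at classroom level is ambiguous. Allocation within classrooms would roughly balance grade; allocation of whole classrooms would not.

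**Calendar.** The problem rests on one side of a contradiction. If cohort 2 runs inside 2026/2027, as other statements have it, the move before T4 disappears. This stands, and it is why the calendar must be settled first.

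**T5.** The growth curves run to T5, by which time three of the four cohort-by-grade groups have left primary school. Transition within the modelled period is therefore common. What is peculiar to cohort 2's 6th graders is that it falls during the programme and before T4.

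**Operations.** Sessions are online, questionnaires go by email, and study staff make the follow-up calls, so T3 and T4 can still be collected. Some friends may move to the same secondary school. Section 4.4 oversamples for loss, section 8.4 allows new dyads after drop-out, and section 10.2 uses FIML. It would go too far to say that the safety route lapses: the PI, the parents and the independent health care professional remain in it. What is unclear is who the teacher-mentor or school-mentor is once a girl has left.

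**Conclusion.** The concern holds as a mismatch between the eligible population and the schedule, tied to a cohort 2 calendar that contradicts itself. The contradiction is certain from the text. The mid-programme school change follows if the stated wave dates are the intended ones and 6th grade is the last primary year.

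The harm is to precision, retention and interpretation: T3 and T4 would describe friendships after a school change in one cohort-by-grade group and friendships still within primary school in the other three. The exposed share is 25% of dyads with equal cohorts and grades, and 16% to 36% if both shares range from 0.4 to 0.6. All of these shares are assumptions, because the protocol gives no split by cohort or grade. How far co-rumination would shift, or how many dyads would separate, cannot be sized from the protocol.

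**What to change.** 1. Reconcile the cohort 2 dates in section 3 (academic year, programme period, wave dates) with section 5.1 and with criterion 3, and state which grades each cohort recruits.
2. If T0 to T4 still crosses the summer and 6th graders are kept, stratify the existing block randomisation by grade within cohort, and include grade and cohort as covariates in the growth models. The covariates may be set out in the SAP.
3. Record at T3, T4 and T5 whether the two girls still attend the same school.
4. Reconcile the teacher-mentor and school-mentor passages in sections 8.3 and 9.2.2 for girls who have left the primary school.

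The cost is a text correction, a few more strata in the randomisation system, and one yes/no item at three waves. Limiting cohort 2 to 5th graders is an option, not a requirement: it avoids the move before T4, but it narrows recruitment and confounds cohort with grade.

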Rationale: Research shows that young adolescent girls who engage in excessive, speculative, and negatively focused discussions with close friends about interpersonal problems and worries — a behaviour also known as co-rumination— face a greater risk of developing internalizing symptoms (i.e., depression and anxiety) and reduced friendship quality. Currently there are no school-based prevention programs available that specifically address high levels of co-rumination in young adolescent girls aged 10-12-years old. Mindfulness training, with a focus on present-moment awareness, appreciation, gratitude, and awareness of the dynamics between thoughts, emotions, bodily sensations, and impulses, in combination with psycho-education, can be helpful for girls who engage in repetitive and judgmental negative interactions. To address this need, we developed a blended, primary school-based mindfulness prevention program called Girls United and the current cluster Randomized Controlled Trial will test program's effectiveness in reducing co-rumination and internalizing problems. Girls United aims to teach mindfulness skills at a dyadic level, i.e., between two close female friends and thereby helps young girls prone to co-rumination incorporate these techniques into their daily lives. This evidence-based prevention program will then be implemented across Dutch primary schools.

Objective: The primary aim of the cluster Randomized Controlled Trial (cRCT) is to evaluate the effectiveness of the Girls United prevention program on self- and parent-reported mental health outcomes in a sample of max 320 young adolescent girls aged 10 to 12 (attending mainstream primary schools in the Netherlands) displaying high levels of self-reported co-rumination. Additionally, the study aims to identify the mechanisms of change of the program.

Study design: The Girls United cluster Randomised Controlled Trial has two arms: (1) an intervention condition in which max 80 girls' friendship dyads ($n = \text{max } 160$ with high levels of self-reported co-rumination) will receive the Girls United program for 14 weeks, and (2) a control condition in which max 80 girls' friendship dyads ($n = \text{max } 160$ with high levels of self-reported co-rumination) will receive teaching-and-care-as-usual (TAU). The intervention will be offered in two consecutive cohorts during academic year 2025/2026 and 2026/2027.

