4.4 Sample size calculation

Multi-level models are used with individuals nested in dyads. To determine the required sample size for this cRCT study power analyses were conducted using Optimal Design Plus – Evidence (Raudenbusch, 2011). These analyses were based on an alpha level (α) of .05, with three measurement points (baseline and two follow-up measurements), and an intraclass correlation (ICC) of .40 between two friends (ρ). This ICC was derived from observed ICCs for perceived support within friendship dyads ($n = 266$ pairs) in an existing dataset of adolescents with an average age of 13. For average risk girls (M), the multilevel power analysis was based on an expected effect size (Cohen's d) of 0.50, indicating a small to medium effect. The power analysis showed that, to achieve a power level of 0.80, at least 122 average-risk friendship dyads would need to be included. However, we will aim to oversample to a maximum of 160 dyads in order to be able to compensate for loss to follow up .

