8.2 Randomisation, blinding and treatment allocation

Dyads will be randomly assigned in a 1:1 ratio to either the intervention group (max 80 dyads; $n = \text{max } 160$ girls) or the control group (TAU; max 80 dyads; $n = \text{max } 160$ girls) by an independent researcher using CASTOR EDC, a web-based randomization program compliant with Good Clinical Practice (GCP) guidelines. Ideally, randomization will occur on a single day after completing the screening phase. If this is not feasible (e.g., due to time constraints), randomisation will proceed in batches of 50 dyads (100 girls) and on classroom level. The median of the screening scores will be calculated, and dyads where one or both girls above the median will be included. These dyads will then be randomly assigned to the intervention or control group using a block randomisation procedure (50% allocated to each group). Allocation will be concealed through a computer-generated list in a secure web-based application. However, due to the organisational structure of the prevention program, participants, parents, schools, and researchers will be aware of group assignments. As the trial follows an open-label design, unblinding will not occur.

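### The inclusion rule admits dyads with only one girl above the median, so it cannot yield the 50% highest scoring girls; the enrolled population is misdescribed in Section 4.2 and the Summary

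*Protocol*

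**What the plan says.** The operative rule is the same wherever it appears. Section 4.2 takes dyads in which "at least one of the two girls, or both girls, have a score above the median co-rumination screening score of the cohort". Section 4.1 defines high risk for the dyad and not the girl, and says that at least one member "should have a score above the median co-rumination screening score of the cohort the dyad belongs". The study population paragraph of the Summary and Section 8.2 use the same at-least-one condition.

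Two places describe the result differently. Section 4.2 follows its rule with "This will result in a sample of the 50% highest scoring girls on co-rumination". The objective in the Summary describes the sample of at most 320 girls as "displaying high levels of self-reported co-rumination", and the study design paragraph attaches the same description to the up to 160 girls in each arm.

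On the cut-off, Sections 4.1 and 4.2 name the cohort median. Section 8.2 prefers randomisation on a single day after screening and, if that is not feasible, allows batches of 50 dyads (100 girls). It then says: "The median of the screening scores will be calculated, and dyads where one or both girls above the median will be included". It does not say whether that median belongs to the cohort or to the batch.

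**The concern.** The rule excludes a dyad only when neither girl is above the median. Every dyad that straddles the median is enrolled whole and brings in one girl who is not a high scorer. The rule and the sentence that summarises it therefore describe two different populations, and the Summary carries the wrong one into the trial objective.

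What is at stake is the population to which the result applies. A report that follows the Summary would claim an effect in girls with high co-rumination, although a substantial minority of those analysed would not fit that description. The screener is also the primary outcome instrument (Section 8.1.1), so the mismatch would show in the baseline table.

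There is a smaller, related gap. If a batch were randomised before its cohort had been fully screened, the cohort median would not yet exist, and Section 8.2 does not say what would then be used.

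**Working it through.** **Inputs**
- Rule: a dyad qualifies if one or both girls are above the cohort median (Sections 4.1, 4.2, 8.2).
- Stated result: the top 50% of girls, that is, no enrolled girl at or below the median (Section 4.2).
- Friend correlation: Section 4.4 uses "an intraclass correlation (ICC) of .40 between two friends". It adds: "This ICC was derived from observed ICCs for perceived support within friendship dyads". Applying it to the co-rumination screener is an assumption, so a range is given.
- Score: mean of nine items scored 0 to 4 (Section 8.1.1), so 9 × 4 + 1 = 37 possible values, and ties at the median can occur.

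**Step 1: no distribution assumed.** Ignore ties and let p be the share of screened dyads with exactly one girl above the median. Half of all girls are above it, so the shares with both above and with neither above are each (1 − p)/2. Then:
- dyads qualifying = 1 − (1 − p)/2 = (1 + p)/2
- enrolled girls not above the median = (p/2) / ((1 + p)/2) = p/(1 + p)

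The stated result needs p/(1 + p) = 0, hence p = 0: no friends may ever fall on opposite sides of the median. Under bivariate normality that means a correlation of exactly 1. The plan's figure is not reproduced for any lower value.

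**Step 2: size at correlation 0.40, bivariate normal.**
- P(neither above) = 1/4 + arcsin(0.40)/(2π) = 0.3155
- dyads qualifying = 1 − 0.3155 = 0.6845, or 68.5%
- p = 1 − 2 × 0.3155 = 0.369
- enrolled dyads with only one girl above = 0.369/0.6845 = 53.9%
- enrolled girls not above = 0.539/2 = 27.0%, about 86 of 320

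**Step 3: range over the correlation.**

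| Friend correlation | Dyads qualifying | Enrolled girls not above median |
|---|---|---|
| 0 | 75.0% | 33.3% |
| 0.2 | 71.8% | 30.4% |
| 0.4 | 68.5% | 27.0% |
| 0.6 | 64.8% | 22.8% |
| 0.8 | 60.2% | 17.0% |
| 1 | 50.0% | 0% |

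**Step 4: ties.** A simulation with a 37-level score at correlation 0.40 (assumed mean 1.6, SD 0.6 to 1.0) gave about 68% of dyads qualifying and 27% of enrolled girls at or below the median, of whom 22% to 24% of enrolled girls were strictly below. For that reason the text says not above the median and avoids the word below.

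**Step 5: the cut-off, conditionally.** If each batch of 50 screened dyads were judged on its own median, simulation at correlation 0.40 puts the SD of that median at about 0.14 score SD, with 95% of batch cut-offs between about the 39th and 61st population percentiles. This applies only if batch medians are used, which Section 8.2 does not say.

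**The case against.** The best defence is that eligibility is not in doubt. The at-least-one rule is consistent across the Summary's study population paragraph and Sections 4.1, 4.2 and 8.2, and Section 4.1 places high risk at dyad level. On that view there is one loose sentence in Section 4.2 and loose wording in the Summary. This is fair as a description of the extent, and it limits the remedy to wording. It does not rescue the sentence, which is wrong as written, nor the objective, which names the population for the conclusion.

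The figures can also be challenged, since the 0.40 is for perceived support in adolescents averaging 13 years, not for this screener at ages 10 to 12. That stands, and is why the range is needed. No value in it approaches the stated result.

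Three stronger readings are tempting and should not be drawn.
- **Loss of power.** A reader might infer that girls not above the median dilute the assumed effect. Section 4.4 sets d = 0.50 for average-risk girls, not for a top-half sample. Under the Step 2 assumptions the enrolled girls would average (1 + 0.4)/(2√(2π))/0.6845 = +0.41 SD on the screener, which is above average risk. Nothing in the protocol supports a smaller effect in part of the sample.
- **A cut-off that does move.** Batching is a fallback, and Section 8.2 never says that the median is recomputed. If only the randomisation is split after screening is complete, the cut-off stays put.
- **Bias between arms.** Eligibility is settled before allocation, so even a varying cut-off would not bias the comparison.

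**Conclusion.** The concern holds as a misdescription of the enrolled population. The claim in Section 4.2 contradicts its own rule unless no dyad straddles the median, and this conclusion needs no distributional assumption beyond the absence of ties. The size does rest on assumptions: with bivariate normal scores and a correlation of 0.40, about 68% of screened dyads qualify and about 27% of enrolled girls are not above the median, with ranges of 60% to 75% and 17% to 33% for correlations from 0.8 to 0.

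The batch point holds only as an omission: Section 8.2 does not say which median applies, so the cut-off could move if a batch is randomised before cohort screening is complete. Randomisation, the comparison of arms and the sample size are not called into question by this point.

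**What to change.** 1. In Section 4.2, replace the 50% sentence with a dyad-level statement: the sample consists of dyads with at least one girl above the cohort median. Add the expected share of girls not above it (about 27% at a correlation of 0.40, with the range and the source of that correlation).
2. In the Summary, change the objective and the study design paragraph so that high risk describes the dyads and not every girl. State that conclusions are drawn for high-risk dyads.
3. In Section 8.2, state that the cohort median of Sections 4.1 and 4.2 applies to every batch and that no batch is randomised on its own median.

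Items 1 and 2 cost only wording. Item 3 means that a cohort's screening must be complete before its first batch is randomised, which may cost some time if batching was meant to start earlier.

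Selecting on the dyad mean score would not repair the sentence. At a correlation of 0.40 a girl's score correlates √0.7 with her dyad mean, so the share above the median among selected girls would be 2 × [1/4 + arcsin(√0.7)/(2π)] = 0.816, leaving about 18% not above it. Correcting the description is enough.
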